7 PARTICIPANT TIMELINE

Students will be informed about the trial prior to the start of the semester for which they are eligible (orientation week for VP and 1st semester cohorts, and at the end of 4th semester for 5th semester cohorts). Students will be recruited into the study during orientation week and/or the first week of the semester, and will receive the first injection (day 0) within the first two weeks of the semester. Participants will receive the second injection on day 7 and the third injection on day 21. If necessary, participants can begin the intervention later, so long as day 0 falls within the first 12 weeks of the semester (see **Section 5.2.2, Exclusion criteria** for details).

Weekly illness surveys will begin in study week 3 (Monday of study week 3, day 10-14 after first injection) for all participants, and will continue for 26 weeks (through week 11 of the following semester in the case of a two-week semester break, or week 10 of the following semester in the case of a three-week semester break). One week after receipt of the final (26th) weekly survey, participants will be unmasked and will exit the study. Following exit, participants who were allocated to the control group will begin a primary course of rabies

vaccine in weeks 11 or 12 (depending on 3- or 2-week semester break), to be completed by the end of the semester (weeks 14 or 15).

A participant is considered to have completed the study one week after receipt of the final (26th) weekly survey.

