7.2 LOST TO FOLLOW-UP

A participant will be considered lost to follow-up if s/he fails to complete a weekly survey for more than three consecutive weeks and is unable to be contacted by the study personnel. Contact will be by email to the participant's registered RUSVM email address. The participant will be considered unreachable if s/he does not respond after 3 emails. At this point, s/he will be considered to have withdrawn from the study with a primary reason of lost to follow-up.

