8 SAMPLE SIZE

The estimated number of participants needed to achieve the study's primary objective is 430 (215 in each group). The sample size was calculated using the approach for comparing two negative binomial rates based on true rates (Approach 2 in [17]), implemented using the function *power.nb.test* in package 'MKmisc' in R, and assuming the following parameter values:

- Alpha level = 0.05
- Targeted power = 0.8
- Event rate for control group = 2 (expected mean number of new CID episodes [composite primary endpoint] over 26 weeks)
- Rate ratio under alternative hypothesis = 0.75
- Average length of participation (accounting for drop-out and non-response) = 21 weeks (0.8 of 26-week observation period)
- Negative binomial dispersion parameter (k in [17]) = 0.4

The three nuisance parameters (average length of participation, event rate for control group and negative binomial dispersion parameter) were estimated from data collected over 7 weeks of a pilot study of rates of CID episodes in 90 RUSVM students (40 in 1st semester and 50 in 5th semester) from 21 May to 8 July, 2018 (weeks 3 through 9 of summer semester).

An internal pilot study will be done using data from the first 300 participants to complete the study. As the expected enrollment rate is <100 participants per semester, this will allow capture of seasonal variation in event rates (≥ 3 semesters in internal pilot study). The three nuisance parameters will be re-estimated from the internal pilot study data and the sample size recalculated, using a blinded sample size re-estimation method for count data [18, 19], which maintains required power without an increase in the type I error. The sample size will only be increased and not decreased on the basis of the internal pilot study (that is, if the recalculated sample size is smaller than the original sample size, the original sample size will still be used).

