11.3 BLINDING (MASKING)

Participants will be blinded to their study arm allocation. The intervention procedure will be identical for both arms (intramuscular injections at Student Health Services on days 0, 7 and 21). Participants allocated to the control group will receive an intramuscular injection

of sterile water for injection using identical syringes and needles as for the vaccine group.

The injection will be prepared in a separate room to maintain participant blinding.

Unblinding of participants will occur in circumstances in which there is a need to determine their rabies pre-exposure vaccination status; for example, in the event of a possible rabies exposure or if participants wish to undertake activities during the course of their participation in the study that would increase their risk category of rabies exposure.

Rabies post-exposure management differs between patients who have not been previously vaccinated and those who have been previously vaccinated. The ACIP-recommended treatments for patients who have not been previously vaccinated [16] are rabies immune globulin (RIG) infiltrated around the wound (if present), and four injections of rabies vaccine (one each on days 0, 3, 7 and 14). For previously-vaccinated patients, ACIP recommends that no RIG should be administered, and only two injections of rabies vaccine (one each of days 0 and 3). Thus, in the event of a suspected rabies exposure that requires post-exposure prophylaxis, participants should establish their vaccination status as soon as possible.

Participants can determine their vaccination status by contacting the Student Health Services to request access to their health records, or by contacting study personnel with access to the 'Participant allocation file' and/or Visit 1 CRF (Principal Investigator, Study Coordinator, study personnel at Student Health Services). Steps for determining vaccination status and emergency contact details of all relevant personnel will be provided

in the informed consent document and in the weekly survey sent to participants.

Participants who are unblinded will exit the study at that point.

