12 DATA COLLECTION METHODS

After enrollment, participants will complete a questionnaire that will capture data on relevant baseline characteristics including sex, age, health and vaccination status. (Baseline CRF; Appendix C). Participants will complete a short survey each week, starting in study week 3, to capture self-reported episodes of illness (respiratory, diarrheal and febrile illness; Primary Endpoint and Secondary Endpoints 1-5) in the preceding week (Appendix G). Surveys will be sent by email to all participants each Monday. Participants who have not completed the survey by Wednesday afternoon will be sent a request by email to complete the survey for the preceding week. Surveys will be sent weekly, for 26 weeks. A participant is considered to have completed the study one week after receipt of the final (26th) weekly survey for that participant's cohort.

As an incentive to enhance participant retention and response rates in weekly illness surveys, all participants who complete a weekly survey will be entered into a draw each week for a chance to win a EC\$25 gift voucher to a food/beverage vendor on the RUSVM campus. Selection of a winner each week will be done by computer-generated random sampling. The weekly winner will be notified by email in the week following the draw.

Clinically- and laboratory-confirmed episodes of study syndromes (Secondary Endpoints 6 & 7) will be collected by study personnel at RUSVM Student Health Services, as part of the

routine clinic visits and diagnostics. At the end of each 26-week observation period for each study cohort, data from that cohort will be compiled by the director of the RUSVM Student Health Services, anonymized to protect privacy and aggregated by study arm, before being sent to the Data Analyst who will conduct the analysis.

Occurrence of expected Adverse Events (Safety Endpoint 1) will be solicited in an online survey (Appendix H) sent to participants 3 days after receiving an injection (for dose 1, 2 and 3). Occurrence of unsolicited adverse events and serious adverse events (Safety Endpoint 2) will be captured by study personnel at RUSVM Student Health Services through completion of an Adverse Event form (Appendix I; See **Section 15.3, Identification of Adverse Events** for details).

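### Section 8 re-estimates participation, including drop-out, from study completers only; read literally, a needed sample size increase can be understated or missed

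*Combined protocol and SAP*

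**What the plan says.** Section 8 plans 430 participants (215 per arm), using three nuisance parameters: the control event rate, the negative binomial dispersion, and participation, given as "Average length of participation (accounting for drop-out and non-response) = 21 weeks", or 0.8 of the 26-week period. These values "were estimated from data collected over 7 weeks of a pilot study" in 90 students within one semester.

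All three are to be re-estimated, blinded, during the trial: "An internal pilot study will be done using data from the first 300 participants to complete the study". The adjustment runs one way: "The sample size will only be increased and not decreased on the basis of the internal pilot study".

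Completion is defined in Section 7: "A participant is considered to have completed the study one week after receipt of the final (26th) weekly survey". Section 12 gives the same definition but ends it with "one week after receipt of the final (26th) weekly survey for that participant's cohort". Section 7.2 says of a participant who stops responding and cannot be reached that "s/he will be considered to have withdrawn from the study with a primary reason of lost to follow-up". Section 11.3 adds: "Participants who are unblinded will exit the study at that point". Section 14 times the final analysis by each participant having either completed or withdrawn, so it treats these as alternative outcomes.

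**The concern.** A set made up only of completers contains no drop-out, so it cannot estimate a quantity that is supposed to include drop-out. Missed surveys among people who stay to the end are still captured; weeks lost because someone left are not. Estimated participation is then too high, and the recalculated sample size too low.

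This matters because the planning value of 0.8 rests on 7 weeks of data. The trial follows each participant for 26 weeks, across a semester break and into the next semester. The internal pilot is the first point at which drop-out over that span can be seen. Section 8 says the re-estimation method preserves the required power, and that aim fails if one of its three inputs is biased in the unsafe direction.

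**Working it through.** **Inputs.** From Section 8: control rate r = 2 per 26 weeks, rate ratio 0.75, participation t = 0.8, dispersion k = 0.4, power 0.80, alpha 0.05. Two-sided testing is from Section 14 and 1:1 allocation from Section 11.1.

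**Formula** (two negative binomial rates, variance at the true rates):

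n per arm = (1.960 + 0.842)² × V / (ln 0.75)², where V = (1/t)(1/r + 1/(0.75 r)) + 2k.

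The multiplier is 7.849 / 0.08276 = 94.84.

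**The plan's own figure.** V = (1/0.8)(0.5 + 0.6667) + 0.8 = 2.258, so n = 94.84 × 2.258 = 214.2. That rounds up to 215 per arm, 430 in total, as Section 8 states. Power at 215 is 80.2%.

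**Effect of a completer-only estimate.** Take the recalculated n as max(215, n at the completers' t), and evaluate power at the true t:

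Power = Φ(√n × |ln 0.75| / √V − 1.960).

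Rate and dispersion are assumed to be re-estimated correctly. The departures from the planning values are assumptions, chosen to show a range. The implied drop-out d assumes uniform leaving times and equal response before leaving, so that true t = completer t × (1 − d/2).

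| Rate, k | True t | Completer t | Implied drop-out | n needed per arm | n obtained per arm | Power |
|---|---|---|---|---|---|---|
| 2, 0.4 | 0.80 | 0.80 to 0.95 | 0 to 32% | 215 | 215 | 80.2% |
| 1.5, 0.4 | 0.80 | 0.85 | 12% | 261 | 250 | 78.4% |
| 1.5, 0.4 | 0.80 | 0.90 | 22% | 261 | 240 | 76.7% |
| 1.5, 0.4 | 0.80 | 0.95 | 32% | 261 | 232 | 75.3% |
| 2, 0.6 | 0.80 | 0.85 | 12% | 253 | 244 | 78.7% |
| 2, 0.6 | 0.80 | 0.90 | 22% | 253 | 237 | 77.5% |
| 2, 0.6 | 0.80 | 0.95 | 32% | 253 | 231 | 76.5% |
| 2, 0.4 | 0.75 | 0.80 or more | at least 12.5% | 224 | 215 | 78.5% |
| 2, 0.4 | 0.70 | 0.80 or more | at least 25% | 234 | 215 | 76.6% |

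Worked example, second-to-last row: at t = 0.75, V = (1/0.75)(1.1667) + 0.8 = 2.356 and n = 223.4, so 224 are needed. Completers showing t = 0.80 return 214.2, so the trial stays at 215.

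The first row is harmless. In the next six rows the increase is understated, and in the last two it is missed.

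**The case against.** The strongest reply is that the 300 is a maturity trigger and does not select who is analysed. Section 8 justifies the number by the seasons it covers, and the cohort wording in Section 12 makes completion look like a calendar event. An analyst who re-estimates participation as Section 8 defines it would have to count drop-out. This reading is possible. But Section 8 does not state it, the definition in Section 7 lacks the cohort wording, and Section 14 separates completers from those who withdraw. Two analysts could build different pilot sets from the same text.

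Three further points stand and limit the size of the problem:

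- Poor responders who can be reached and do not withdraw still count as completers, so their missed weeks lower the estimate as they should. Unreachable non-responders do not, because Section 7.2 classes them as withdrawn.
- The documents do not split the 20% loss. With a small gap (completers 0.82, true 0.80) power is 79.3% at rate 1.5 and 79.5% at k = 0.6.
- Even on the literal reading, re-estimation helps. At rate 1.5 and k = 0.4, power is 72.1% with no increase, 76.7% with a completer-only estimate of 0.90, and 80.1% with the correct value.

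The type I error rate and the primary analysis, which uses weeks observed as an offset, are not in question. How the two cited methods papers handle unequal follow-up cannot be checked from the documents.

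**Conclusion.** The concern holds. As written, the rule leaves drop-out out of an estimate meant to include it, and nothing in the documents corrects this. The consequence is confined to power, and arises only when the true requirement exceeds 430. In the adverse scenarios shown, power is about 1.3 to 4.7 points below the 80% target (78.7% to 75.3%); smaller gaps cost less, down to nothing. These figures assume that rate and dispersion are re-estimated without bias, and they use illustrative values for rate, dispersion and the share of loss due to drop-out. The sentence should be corrected before the re-estimation is done, because it governs a decision that can change the sample size.

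**What to change.** In Section 8, define the internal pilot as the first 300 randomized participants whose scheduled 26-survey period has elapsed, including everyone who withdrew, was lost to follow-up or was unblinded. Estimate average participation as completed survey weeks divided by 26, averaged over all 300. Estimate the blinded event rate and dispersion from the same 300, with weeks observed as the offset.

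This is one short change. It stays blinded, needs no new data, and triggers the review no later than waiting for 300 completers would. There are two costs:

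- The recalculated size may be larger. At rate 1.5, true participation 0.80 and completer participation 0.90, it is 2 × 261 = 522 instead of 2 × 240 = 480, with expected enrollment below 100 per semester.
- The pilot carries fewer observed weeks: 300 × 26 × 0.80 = 6,240 against 300 × 26 × 0.90 = 7,020. Rate and dispersion are therefore estimated slightly less precisely.

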9 RECRUITMENT

The PI or Study Coordinator will present information on the study to VP and 1st semester students during their orientation week prior to the start of their program, and to 5th semester students during their 4th semester. They will be provided with a link to a website that contains more information about the project, including the informed consent documents and contact details of the study personnel. A question-and-answer session with

the PI will be scheduled. Prospective participants will have the opportunity to ask questions via email or in person with the study investigators, either during scheduled information sessions or by appointment.

To compensate study participants for their time and inconvenience, the study will provide the primary course of vaccine at no cost to all participants (participants allocated to the control group [including participants who withdraw or are withdrawn] will receive the vaccine after exit from the study). Current cost of rabies vaccination for RUSVM students is US\$ 200 for a 3-dose primary course.

10 CONSENT

A list of all VP/1st/5th semester student names and email addresses will be obtained from the RUSVM IT Department, and an invitation to join the study will be sent by email to these students. The email will contain a unique link to a survey (Appendix A), which will be used to establish eligibility and seek agreement to participate from eligible students. Initial agreement to participate in the study will be documented electronically as selection of the option, "I agree to participate in the study" for the unique survey linked to the participants identifiers (name, surname and email address). Participants who agree in the online survey will still need to sign a paper copy of the informed consent document (Appendix B) in person with a designated member of the study team (Principal Investigator, Study Coordinator or Nurse Practitioner). Only participants who sign a paper copy of the informed consent document with a member of the study team will be considered enrolled and will be allocated to a study group. A signed and dated copy of the consent form will be

given to the participant. Paper copies of signed consent forms will be collected and stored by the Principal Investigator in a locked file cabinet in an area with limited access (PI's office).

Following enrollment, participants will be given a baseline health questionnaire to complete (Baseline CRF; Appendix C) and will be given instructions to visit the RUSVM Student Health Services Office within the first two weeks of the semester for screening and allocation into one of the two study arms. The completed baseline health questionnaire will be checked by study personnel at RUSVM Student Health Services at Visit 1, collected and stored by the Principal Investigator in a locked file cabinet in an area with limited access (PI's office).

11 ALLOCATION

11.1 SEQUENCE GENERATION

Allocation of participants to study arms will be done by restricted randomization (permuted block design with stratification). Stratification will be by cohort (three cohorts per year: January, May and September) and sex (within cohort). Within strata, randomization will be done by computer-generated randomly permuted blocks of varying size (using the function *blockrand* in the package 'blockrand' in R). Enrolled students will be allocated in a 1:1 ratio to one of the two study arms.

11.2 ALLOCATION CONCEALMENT

Randomization cards will be created by the Principal Investigator or Study Coordinator (using the function *plotblockrand* in the package 'blockrand' in R), placed in opaque envelopes with a window, and sealed, with the sequential subject number (starting from 1 for each sex in each cohort) visible in the envelope window. On the first day of the semester, envelopes will be placed in the RUSVM Student Health Services Office. Envelopes will be drawn sequentially by study personnel at Student Health Services as participants come in for the first injection (day 0), and opened to determine allocation. After the injection is administered, the RUSVM Student Health Services member will complete the Case Report Form for this visit (Visit 1 CRF; Appendix D), including student name, surname, email address, allocation group, intervention actually received, date received, and the batch number and expiry date of the vaccine or diluent. An entry will be also be made in students' health records. Data from the Visit 1 CRF will be entered into a password-protected file ('Participant allocation file') in a restricted-access folder on the RUSVM network. Access to the folder will be restricted to study personnel only. When participants return for the second (day 7) and third (day 21) injections in the course, study staff at RUSVM Student Health Services will refer to the file to determine the participant's allocation. After injection, study personnel will complete CRF Visit 2 (Appendix E) or Visit 3 (Appendix F).

11.3 BLINDING (MASKING)

Participants will be blinded to their study arm allocation. The intervention procedure will be identical for both arms (intramuscular injections at Student Health Services on days 0, 7 and 21). Participants allocated to the control group will receive an intramuscular injection

of sterile water for injection using identical syringes and needles as for the vaccine group.

The injection will be prepared in a separate room to maintain participant blinding.

Unblinding of participants will occur in circumstances in which there is a need to determine their rabies pre-exposure vaccination status; for example, in the event of a possible rabies exposure or if participants wish to undertake activities during the course of their participation in the study that would increase their risk category of rabies exposure.

Rabies post-exposure management differs between patients who have not been previously vaccinated and those who have been previously vaccinated. The ACIP-recommended treatments for patients who have not been previously vaccinated [16] are rabies immune globulin (RIG) infiltrated around the wound (if present), and four injections of rabies vaccine (one each on days 0, 3, 7 and 14). For previously-vaccinated patients, ACIP recommends that no RIG should be administered, and only two injections of rabies vaccine (one each of days 0 and 3). Thus, in the event of a suspected rabies exposure that requires post-exposure prophylaxis, participants should establish their vaccination status as soon as possible.

Participants can determine their vaccination status by contacting the Student Health Services to request access to their health records, or by contacting study personnel with access to the 'Participant allocation file' and/or Visit 1 CRF (Principal Investigator, Study Coordinator, study personnel at Student Health Services). Steps for determining vaccination status and emergency contact details of all relevant personnel will be provided

in the informed consent document and in the weekly survey sent to participants.

Participants who are unblinded will exit the study at that point.

12 DATA COLLECTION METHODS

After enrollment, participants will complete a questionnaire that will capture data on relevant baseline characteristics including sex, age, health and vaccination status. (Baseline CRF; Appendix C). Participants will complete a short survey each week, starting in study week 3, to capture self-reported episodes of illness (respiratory, diarrheal and febrile illness; Primary Endpoint and Secondary Endpoints 1-5) in the preceding week (Appendix G). Surveys will be sent by email to all participants each Monday. Participants who have not completed the survey by Wednesday afternoon will be sent a request by email to complete the survey for the preceding week. Surveys will be sent weekly, for 26 weeks. A participant is considered to have completed the study one week after receipt of the final (26th) weekly survey for that participant's cohort.

As an incentive to enhance participant retention and response rates in weekly illness surveys, all participants who complete a weekly survey will be entered into a draw each week for a chance to win a EC\$25 gift voucher to a food/beverage vendor on the RUSVM campus. Selection of a winner each week will be done by computer-generated random sampling. The weekly winner will be notified by email in the week following the draw.

Clinically- and laboratory-confirmed episodes of study syndromes (Secondary Endpoints 6 & 7) will be collected by study personnel at RUSVM Student Health Services, as part of the

routine clinic visits and diagnostics. At the end of each 26-week observation period for each study cohort, data from that cohort will be compiled by the director of the RUSVM Student Health Services, anonymized to protect privacy and aggregated by study arm, before being sent to the Data Analyst who will conduct the analysis.

Occurrence of expected Adverse Events (Safety Endpoint 1) will be solicited in an online survey (Appendix H) sent to participants 3 days after receiving an injection (for dose 1, 2 and 3). Occurrence of unsolicited adverse events and serious adverse events (Safety Endpoint 2) will be captured by study personnel at RUSVM Student Health Services through completion of an Adverse Event form (Appendix I; See **Section 15.3, Identification of Adverse Events** for details).

Participants in the vaccine efficacy ancillary study will have a maximum volume of 8 mL of blood collected by venipuncture prior to injection on day -7 (acceptable range -3 through -11), and again on day 180 (acceptable range 173 through 187). Serum will be separated and stored at -20 °C at RUSVM until transport to the laboratory for measurement of RVNA by RFFIT. Serum specimens will be labelled with participant study identification numbers only. No other participant information will be sent to the laboratory.

Participants in the immunology ancillary study will have a maximum volume of 10 mL of blood collected by venipuncture prior to injection on day 0, and again on days 21 and 90. Blood specimens will be immediately taken to the RUSVM Research Laboratory for

isolation of PBMCs. Blood specimens will be labelled with participant study identification numbers only. No other participant information will be sent to the laboratory.

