14 STATISTICAL METHODS

The analysis of the primary endpoint and secondary endpoints 1-7 will be conducted after all randomized participants have completed the study (one week after receipt of the final weekly survey) or have withdrawn from the study, whichever occurs first. Primary analysis will be based on intention-to-treat analysis of all events (that is, not just occurrence of first events). The comparison of incidence rates of CID episodes (primary endpoint and secondary endpoints 1-7) between the treatment arms will be performed using a negative binomial regression model, which accounts for different lengths of observation period. Participants' number of CID episodes will be modelled as a function of treatment group, with the number of weeks of observation included as an offset in the model. This analytic model estimates the rate ratio, λ_t / λ_c , which quantifies the risk of CID episodes associated with rabies vaccination (λ_t) in comparison to placebo injection (λ_c). Statistical significance will be controlled at the 2-sided, 0.05 alpha level, and the estimated rate ratio compared with 1, assuming the following statistical hypothesis:

H_0 (null hypothesis): Rate ratio = 1

H_1 (alternative hypothesis) Rate ratio $\neq 1$

Treatment effect will be based on the coefficient in the model. Statistical significance at the pre-specified alpha level will be based on a Wald testing procedure. CID rates (primary

endpoint and secondary endpoints 1-7) for rabies vaccine and placebo, and the rate ratio, will be presented and will include 95% confidence intervals.

A detailed description of the statistical methods that will be used for the primary and secondary endpoints will be provided in a Statistical Analysis Plan (SAP).

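### A pre-specified covariate for each participant's own recent illness history could add about 0 to 4 points of power at little cost; the trial is not underpowered without it

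*Combined protocol and SAP*

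**What the plan says.** Protocol Section 12 describes the baseline form in summary: "participants will complete a questionnaire that will capture data on relevant baseline characteristics including sex, age, health and vaccination status". The items themselves are in Appendix C, which is not in the text available for review. The only analytic use stated for the form is in Section 3.2.2, where it identifies immunosuppressed participants for a subset analysis.

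For the primary endpoint, Section 14 specifies a negative binomial regression in which the "number of CID episodes will be modelled as a function of treatment group", with weeks of observation as offset and a Wald test. It names no baseline covariate and leaves fuller detail to a separate SAP, also not available here.

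Section 8 plans with "Negative binomial dispersion parameter (k in [17]) = 0.4". This value came from a 7-week pilot in 90 students and is to be re-estimated blind from the first 300 completers. The sample size may then rise but not fall.

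**The concern.** In a negative binomial model, k measures how much true illness rates differ between people beyond Poisson chance. At k = 0.4 the differences are wide, and they make up about a third of the variance in the trial's own sample-size formula. A person's recent episode count is the natural baseline predictor of their later count. If it is asked before allocation and put in the model, part of k moves from noise into explained variation.

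With a log link and a treatment effect common to all participants, the vaccine rate ratio keeps its meaning, so the gain is precision without a change of estimand. A smaller residual k would also carry into the blinded re-estimation and soften any increase in sample size. This is separate from adjusting for the stratification factors, sex and cohort. What is at stake is a few points of power at most.

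**Working it through.** **Inputs from the documents.** Section 8: "Alpha level = 0.05", two-sided by Section 14 ("Statistical significance will be controlled at the 2-sided, 0.05 alpha level"); "Targeted power = 0.8"; "Event rate for control group = 2" per 26 weeks; "Rate ratio under alternative hypothesis = 0.75", so 1.5 on vaccine; average exposure 0.8 of 26 weeks; k = 0.4. Section 11.1: 1:1 allocation.

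**Step 1: reproduce the plan's figure.** With the true-rates variance that Section 8 names:

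- V = (1/0.8)(1/2 + 1/1.5) + 2 × 0.4 = 1.458 + 0.800 = 2.258
- n per arm = (1.960 + 0.842)² × V / (ln 0.75)² = 7.849 × 2.258 / 0.08276 = 214.2, rounded up to 215, or 430 in all. This matches.
- Power at 215 per arm = Φ(√215 × 0.2877 / √2.258 − 1.960) = Φ(0.847) = 80.2%.

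**Step 2: what k = 0.4 implies.** Read as a gamma distribution of personal rates, the coefficient of variation is √0.4 = 0.63, and the central 95% of people lie at 0.17 to 2.57 times the mean rate. The k term is 0.800/2.258 = 35% of V.

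**Step 3: what a 3-month count can explain.** At 2 episodes per 26 weeks, a 13-week window has mean m = 1. Let ρ be the correlation between a person's underlying rate before and after baseline (the stability). The share of k explained is at most R² = ρ² × km/(1 + km) = ρ² × 0.4/1.4. The residual k is 0.4(1 − R²), which goes back into the Step 1 power formula.

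ρ is not in the documents, so a range is shown:

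| ρ (assumed) | R² | residual k | V | power | gain, points |
|---|---|---|---|---|---|
| 1.0 | 0.286 | 0.286 | 2.030 | 84.2% | 4.0 |
| 0.75 | 0.161 | 0.336 | 2.130 | 82.4% | 2.2 |
| 0.5 | 0.071 | 0.371 | 2.201 | 81.1% | 1.0 |
| 0.25 | 0.018 | 0.393 | 2.244 | 80.4% | 0.3 |

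**Step 4: check by simulation.** Gamma-Poisson counts, 1,200 trials per setting, with log(count + 1) as covariate and a 13-week window, gave information gains of 1.11, 1.06, 1.02 and 1.01 at the same four values of ρ. Multiplying 215 by these in the power formula gives gains of 3.9, 2.2, 0.8 and 0.4 points. In a separate simulation (3,000 trials, 12-week window, covariate log(count + 2.5), Monte Carlo standard error about 0.7 points), unadjusted power was 80.5%. Adjusted power was 84.9% with fully stable rates and 81.3% at ρ = 0.5. There was no material loss at low stability.

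**Step 5: imperfect recall.** Steps 3 and 4 assume an exact count. As an illustration, suppose that each past episode is recalled with probability 0.5 (an assumption). Then m falls to 0.5 and R² = ρ² × 0.2/1.2.

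- ρ = 1: R² = 0.167, V = 1.458 + 2 × 0.333 = 2.125, power 82.5%, gain 2.3 points.
- ρ = 0.5: R² = 0.042, V = 1.458 + 2 × 0.383 = 2.225, power 80.7%, gain 0.6 points.

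The gain is roughly halved, to about 0 to 2 points.

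**The case against.** The strongest reply is that nothing is wrong with the plan. The sample size reproduces without a covariate, the Wald test matches the method used to size the trial, and the blinded re-estimation already protects against a larger k. That stands. A reader might infer from the wide heterogeneity that the trial is underpowered or that the primary analysis is flawed. The documents support neither: 430 participants deliver the planned 80%.

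A reader might also expect a gain of about 6 points. That needs a 26-week recall window, fully stable proneness and exact recall: R² = 0.8/1.8 = 0.444, power 86.4%. The 3-month item proposed here does not reach it.

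Stability may well be low. Veterinary Preparatory and 1st-semester students have just arrived, so their history is off-island. k may also absorb class differences, reporting habits and outbreaks. It is imprecise too: at the planning rate the pilot expected only 2 × 7/26 = 0.54 episodes per student. These points shrink the gain, possibly to near nothing.

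Nor can one say that illness history is not collected or will not be used. The list in Section 12 is not exhaustive and includes health, Appendix C is unavailable, and the separate SAP may name covariates. Only the absence of a stated use can be asserted.

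**Conclusion.** This is a cheap improvement, not a shortfall. The primary model as stated makes no use of recent illness history, although k = 0.4 implies large differences between people. With a 3-month count the gain is about 0 to 4 points above 80.2% if recall is exact, and about 0 to 2 if it is imperfect. These figures rest on the Section 8 planning values, on reading k as variation in personal rates, and on assumed stability and recall values that the documents do not supply. The direction is secure, since a covariate measured before allocation cost no material power even at low stability. The size is not. The point is worth taking because it costs little, and it should not be ranked with errors in the plan.

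**What to change.** - **Baseline CRF.** If Appendix C does not already ask it, add one item: the number of separate respiratory, diarrheal or febrile illnesses in the past 3 months. Section 10 has the form checked at Visit 1, where allocation also takes place, so state that the item must be complete before the randomization envelope is opened.
- **Primary model.** Unless the separate SAP already does so, pre-specify log(count + 1) as a covariate in Section 14, before any unblinded analysis. Handle missing values with a missing category.
- **Re-estimation.** Use the same covariate when k is re-estimated blind, so that the sample size and the analysis rest on the same residual k.
- **Sensitivity analysis.** Report the unadjusted model alongside.

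The cost is one question, one covariate, a small change to the re-estimation model, and IRB review under Section 18. If cohorts have already been allocated, the question should not be put to them retrospectively; they would go in the missing category and the gain would be smaller. Recall error also shrinks the gain, but it cannot bias the comparison, because the answer is given before allocation.
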